Enhanced Community-Based Asthma Monitoring Through Novel Technology

Protocol version #1 01.11.23

Study Site Contact Information

Nemours Children's Hospital, Delaware Division of Pediatric Pulmonology [name]								
PI	[name]	[contact]	[contact]					
Co-I	[name]	[contact]	[contact]					

Overview of the Study

The primary objective of the proposed study is to pilot test implementation of a protocol for enhanced asthma monitoring using novel technology, including mobile spirometry and remote study visits, for rural and medically underserved children with persistent asthma in Delaware and to determine its feasibility, acceptability, and accessibility. Additionally, the proposed study aims to explore patient and family demographic characteristics and social factors associated with successful completion of the program and to explore the preliminary effect of the enhanced asthma monitoring program on asthma control and sleepiness as a measure of daytime functioning.

Scientific Rationale

Asthma is the most common chronic disease of childhood with significant morbidity, mortality, and economic burden in the United States and in Delaware. Asthma affects up to 6 million children in the United States (US) with estimated healthcare costs of \$81 billion annually.^{1,25} Despite the significant financial resources utilized for asthma and despite advances in preventative medications, asthma-related deaths continue to occur with over 3,000 deaths annually in the US.¹ DE, in particular, is a national asthma hotspot with a higher than average prevalence of childhood asthma(12%).² Over 25% of DE high school students report a lifetime diagnosis of asthma, with even higher rates for racial and ethnically minoritized children. Of those children with asthma in DE, 65% experienced an asthma-related visit to their doctor in the past year.^{2,26}

Asthma disproportionally affects minoritized and underserved children who are also less likely to receive specialty care and routine lung function measurements. In the US, asthma burden disproportionally affects minoritized and economically disadvantaged children with higher rates among non-Hispanic Black children (14.5%) compared to non-Hispanic White (8.2%) children.¹ There are also higher rates of asthma among individuals of lower socioeconomic status¹ and children who live in rural areas.²⁷ Rates of asthma-related deaths are twice as high for Black Americans compared to White Americans (21.8 v. 9.5 deaths per million).¹ Among children with asthma in DE with near-fatal asthma requiring ECMO support, 100% were Black and utilized Medicaid as insurance.²⁸ The reasons for these disparities are multifaceted, but include reduced access to specialty asthma care, 29,30 financial and transportation constraints, 31 and beliefs about medications and selfmanagement.³⁰ Specialty care is associated with better outcomes for youth with asthma.^{32,33} NHLBI guidelines recommend both specialty care and spirometry, a type of lung function testing, as standard components of the diagnosis and management of asthma.¹⁰ Spirometry provides objective measures of lung function and is necessary to monitor asthma control and response to therapy, especially in children, who may not perceive or report ongoing asthma symptoms.³⁴ Although guidelines recommend routine measurements of lung function,¹⁰ current devices available for home use are peak flow meters, which may be inaccurate or even underestimate asthma symptoms.35,36

Chronic and uncontrolled asthma causes daytime and nighttime symptoms and increases risk for severe exacerbations that may be life-threatening. These chronic symptoms are associated with missed school and work days,³⁻⁵ decreased quality of life,^{3,36} and daytime sleepiness.⁶⁻⁹ Improving asthma control has the potential to improve daytime sleepiness and quality of life in children with asthma.⁹ Therefore, novel and innovative approaches to enhance asthma monitoring and access to specialty care, in ways that are acceptable and convenient to families, may be transformative for youth with asthma.

Technology-enhanced interventions have the potential to empower families to monitor asthma more closely and reduce disparities in asthma care. The use of telehealth for specialty care visits and mobile spirometry for monitoring asthma symptoms has the potential to improve outcomes among children from rural and underserved areas by reducing the burdens of time and travel to specialty care centers. The use of telehealth has been studied in children with asthma with some studies showing non-inferiority to standard in-person visits and high patient satisfaction.³⁸ Additionally, small, uncontrolled studies have shown improved symptom control;^{39, 40} however, lack of objective measurements of lung function, typically gathered during in-person visits, may reduce the effectiveness of telehealth visits. This limitation of telehealth care, however, may be surmounted by

the increased availability of hand-held, mobile spirometers that allow for monitoring of airway function in the home setting and provide objective data to both patients and care teams. Preliminary data show positive acceptance and feasibility of using this novel technology with children with asthma and CF.¹⁷⁻²¹ However, there are limited data regarding the use of mobile spirometers in children. In particular, there is little data regarding their use in children from rural and underserved areas, a group at higher risk for asthma-related morbidity and mortality due to decreased access to care. The utilization of technology-enhanced monitoring for asthma in the home setting is a novel approach to engaging patients and families in specialty care without the excessive burden of travel and time. Prior to large-scale interventional studies, it is imperative to assess the feasibility, accessibility, and acceptability of this approach as well as any unique concerns regarding the use of such technology specific to this population.

Recruitment and Enrollment

Study Eliaibility

- Children with persistent asthma (defined as using at least one controller medication or asthma) ages 12-17
- Followed by Nemours Pulmonology and by a primary care practice which meets HRSA criteria as rural or medically-underserved
- Participants must be able to speak and read English.
- Access to a mobile device with internet connectivity
- Ability to follow directions to perform study measures

Exclusion criteria

- Significant cardiopulmonary disease other than asthma (Examples: Cystic Fibrosis, complex congenital heart disease)
- Non-English Speaking

Enrollment targets

• 15 participants

Identifying and Recruiting Participants

A member of the research team will contact eligible participants by telephone and provide a brief summary of the study after review of EMR.

If the potential participant expresses interest in participation, the initial research visit (including consent/assent discussion and documentation and completion of initial study measures) will be scheduled at the Milford or Wilmington outpatient pulmonology office.

Study Procedures

This technology-enhanced asthma pilot study will be completed over 24 weeks using a hybrid approach with remote and in-person research visits. Participants with persistent asthma ages 12-17 will be recruited from Nemours DE Healthcare System Pulmonology Division.

The initial (week 0) and final (week 24) visits will be completed as in-person visits in the Wilmington or Milford, DE, Nemours outpatient pulmonology office. At the initial visit, study measures will be completed, and

participants will be trained on the use of technology for future remote visits (mobile spirometry device connected to mobile application for reporting of results and the use of the telehealth platform). At the initial study visit, in office (gold standard) spirometry will be completed as well as mobile spirometry. Interval monthly visits at weeks 4, 8, 12, 16, and 20 will be completed using remote study procedures with completion of mobile spirometry and measures of asthma control and sleepiness. See Table 1 for study timeline. The final study visit at week 24 will include similar procedures as week 0, including in-office spirometry.

After completing consent/assent procedures during study visit 1, baseline study procedures including standard spirometry using clinic-based pulmonary function equipment (Carefusion Vitalmax[™]), mobile spirometry (using the MIR Spirobank Smart[™] spirometer with the Zephyrx Breath Easy[®] mobile application) will be completed, as well as training on the mobile spirometry device and telehealth application. If participants are unable to complete reliable spirometry (either standard or mobile after 8 attempts and meet standard ATS criteria for acceptable technique), are unable to understand study measures, or if there are any other concerns about participation, the participant will be considered a screen failure and the reasons for screen failure recorded.

At the time of the initial study visit, participants will receive the mobile spirometry unit and will be instructed on the use of a mobile application for results report generation for future visits. The initial study visit will take approximately 2 hours for baseline testing, training, and collection of data. Subsequent study visits will be completed at 4-week intervals using a remote video platform with a member of the research team available to help complete study measures and, if needed, "coach" the participant during completion of mobile spirometry (see Table 1). The participants will be instructed to complete mobile spirometry using the mobile spirometer and the application for generation of results. The participant will be given 8 attempts to complete successful mobile spirometry. Although the remote application does provide instruction and some immediate feedback to the user, the research team member will be available on video for the remote visit for immediate feedback and guidance if there are difficulties obtaining the correct technique or technical concerns. If the participant is unable to achieve reliable results within 8 attempts, the participant will be instructed to stop testing at that time, and additional participant-specific re-training/education will be completed. Time for mobile spirometry completion is expected to be 5-10 minutes. Reasons for inability to complete the mobile spirometry (e.g. technical concerns, patient effort) will be recorded at each visit.

The estimated time for the remote visit is estimated to be 20-30 minutes. The study-specific Satisfaction and Usability Questionnaire will be completed at each visit, which will take approximately 5 minutes to complete. The study-specific demographic and psychosocial assessment tool will be completed at the baseline visit, which will take approximately 5-10 minutes to complete. The asthma history questionnaire will be completed at the baseline and final visit, which will take 5 minutes to complete. The 5-time asthma control test (ACT[®])²³ will be completed at each study visit as well as the 10-item Epworth Sleepiness Scale for Children and Adolescents (ESS-CHAD).²⁴ Participants will receive a pre-paid gift card at the time of study consent, which will be loaded with \$25 after each in-person study visit and \$10 after each remote visit (\$100 total for completion of all visits).

All paper forms used in the study (e.g., questionnaires) will be kept in a locked file cabinet. Only members of the research team will have access to the human subjects' data and identifying information. All data will be identified only by Subject ID and the master list linking the subjects' identities to the code numbers, as well as consent forms with participant names, will be kept in a password protected excel sheet on the Nemours secure server. All electronic study data will be stored in a folder on the Nemours secure shared drive, separate from the document linking participants to subject IDs, and only study personnel will have access to this folder.

Table 1. Study Timeline

Outcome measure	*Baselin e	**Study visit 2	**Study visit 3	**Study visit 4	**Study visit 5	**Study visit 6	*Final	
Time (Weeks)	0	4	8	12	16	20	24	
Demographic and Psychosocial Assessment tool	x							
Asthma history questionnaire	Х						Х	
Standard Spirometry	Х						Х	
Mobile Spirometry	Х	Х	X	Х	X	Х	Х	
Asthma Control Test [®]	Х	Х	X	Х	Х	Х	Х	
Epworth Sleepiness Scale (ESS-CHAD)	Х	X	X	Х	X	Х	Х	
Satisfaction and Usability Questionnaire		x	x	x	x	x	x	
*Visit and Measures will be completed in-person								

**Remote study visit using telehealth platform and mobile spirometry device

Statistical Considerations

The primary outcome of **feasibility** will be evaluated by calculating recruitment and retention rates at each study time point (e.g. percent of approached individuals who consent to participant, percent of enrolled participants who complete each study visit). The percent of patients who are successful at producing mobile spirometry results at each study visit will be calculated. The percentage of participants who require additional training sessions due to difficulty using the device will be calculated. To measure **acceptability**, the Satisfaction and Usability Survey will be reviewed at the item-level, and specifically, responses of "agree" or "strongly agree" will be used as benchmarks of acceptability and feasibility of each item. Responses to the open-ended questions will be analyzed for consistent themes across participants. Finally, to measure **accessibility**, the investigators will measure the length of time required to complete all visits and the frequency of any technical or connectivity issues. The investigators will meet regularly to review data management procedures and discuss any errors. Prior to beginning analyses, the investigators will examine the distribution of the data and identify any potential outliers. The investigators will consult closely with the REACH Center biostatistician in analyzing the data.

Descriptive and comparative statistics will be employed to characterize patient factors associated with successful study completion (completion of \geq 80% of study measures). Categorical variables will be summarized by frequencies and percentages, and continuous variables summarized by mean and standard deviation. Correlations will be utilized to determine whether any patient factors (e.g. age, grade in school, severity of asthma) are associated with successful completion of the pilot (completion of \geq 80% of study measures). For specific Aim 3, changes in asthma control and sleepiness will be examined longitudinally for each participant. Data distributions and change over time will be evaluated. Mean differences will be tested for statistical significance using ANOVA.

REFERENCES:

- 1. (CDC). Most Recent National Asthma Data: National Center for Environmental Health; 2020 [cited 2022 October 5]. Available: https://www.cdc.gov/asthma/most_recent_national_asthma_data.htm.

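### Should the plan compare mobile with in-office spirometry, and describe lung function over time, because both tests are done at weeks 0 and 24?

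*Combined protocol and SAP*

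**What the plan says.** Study Procedures in the combined protocol and SAP schedules two kinds of spirometry. For week 0: "At the initial study visit, in office (gold standard) spirometry will be completed as well as mobile spirometry". For week 24: "The final study visit at week 24 will include similar procedures as week 0, including in-office spirometry". Table 1 marks standard and mobile spirometry at both of these visits, with the footnote "Visit and Measures will be completed in-person", and mobile spirometry alone at weeks 4 to 20.

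Study Procedures also sets quality rules. The screen-failure rule begins "If participants are unable to complete reliable spirometry (either standard or mobile after 8 attempts and meet standard ATS criteria for acceptable technique". At remote visits, a participant "unable to achieve reliable results within 8 attempts" stops testing and is retrained, and the reason for a failed mobile test is recorded at each visit.

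Statistical Considerations uses spirometry as follows: "The percent of patients who are successful at producing mobile spirometry results at each study visit will be calculated". It adds the percent needing further training because of difficulty with the device. It also defines successful completion as at least 80% of study measures, and Table 1 lists both spirometry types among the measures. For change over time it says: "For specific Aim 3, changes in asthma control and sleepiness will be examined longitudinally for each participant". No spirometry variable is named anywhere.

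**The concern.** A test that the protocol calls the gold standard is done beside the device under study at two visits, and no analysis sets the two readings side by side. The week 24 in-office value has no named analysis. The week 0 value at least serves the screen-failure check.

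The Scientific Rationale sharpens the point. It says spirometry "is necessary to monitor asthma control and response to therapy, especially in children, who may not perceive or report ongoing asthma symptoms", and it presents mobile spirometers as the answer to telehealth's lack of objective lung-function data. A reader could therefore expect the pilot to show that the mobile values can be trusted, and to put a lung-function result beside any change in asthma control. As written, the report could give a high percent of successful mobile tests and say nothing about agreement with the clinic value. Acceptable technique does not by itself show that two devices agree.

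**Working it through.** The plan gives no power, precision or SD figure, so there is nothing of its own to reproduce. Three checks apply.

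**1. Does any stated aim need the readings?** The aims come from Overview of the Study and the analyses from Statistical Considerations.

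| Stated aim | Stated analysis | Needs a spirometry value? |
|---|---|---|
| Feasibility | recruitment, retention, percent producing a mobile result, percent retrained | No, only whether a result was obtained |
| Acceptability | questionnaire items and open-ended themes | No |
| Accessibility | visit time, technical and connectivity problems | No |
| Factors linked to completion | descriptive and comparative statistics, correlations with the 80% variable | No, only whether the test was done |
| Asthma control and sleepiness | longitudinal change, ANOVA | No, if asthma control means the Asthma Control Test |

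The last reading is the likely one, because Study Procedures lists mobile spirometry separately from the measures of asthma control.

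**2. Does spirometry count in the analysis at all?** Table 1 schedules 1 + 2 + 2 + 7 + 7 + 7 + 6 = 32 measurements per participant, of which 2 standard + 7 mobile = 9 are spirometry. If the 80% variable counts these entries (an assumption), a participant who missed all spirometry would reach 23/32 = 72% and fall short. The text has the satisfaction questionnaire at every visit; with a baseline copy added, the figure is 24/33 = 73%, with the same result. So the week 24 in-office test plausibly has a use as a completed measure, though its value has no named analysis.

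**3. What would the added analyses deliver?** With full retention there are 15 × 2 = 30 paired sessions and 15 × 7 = 105 mobile sessions. At one visit with n pairs, in units of the SD of the mobile minus in-office differences:

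- Half-width of the 95% CI for the mean difference: t(0.975, n−1)/√n
- Half-width of the 95% CI for each limit of agreement: t(0.975, n−1) × √(1/n + 1.96²/(2(n−1)))

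| Pairs | t | Mean difference | Each limit of agreement |
|---|---|---|---|
| 15 (no dropout) | 2.145 | 2.145/√15 = 0.55 | 2.145 × √(0.0667 + 0.1372) = 0.97 |
| 12 (assumed 80% retained) | 2.201 | 2.201/√12 = 0.64 | 2.201 × √(0.0833 + 0.1746) = 1.12 |
| 10 (assumed 67% retained) | 2.262 | 2.262/√10 = 0.72 | 2.262 × √(0.1000 + 0.2134) = 1.27 |

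Each limit lies 1.96 SD from the mean difference, so an uncertainty of about 1 SD on it is large. The first formula also gives the precision of a week 0 to 24 change in lung function: 0.55, 0.64 or 0.72 SD of the change scores.

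**The case for a change.** The case for a change is that the extra analyses need no further visits, tests or staff. The rationale rests on objective measurement, and the Scientific Rationale asks for concerns specific to this population to be examined before large studies. Stating the use of the readings in advance would also limit selective reporting of lung-function results. The general sentences do not clearly fill the gap. Summarising continuous variables by mean and SD sits in the paragraph on completion factors, and the sentence on change over time follows directly on Aim 3, which names only asthma control and sleepiness.

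Much of this stands. No agreement analysis is stated, no lung-function variable is named, and even a generous reading of the general sentences yields no paired comparison.

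It does not show that a stated method fails. What the Scientific Rationale says must be assessed before large studies is feasibility, accessibility and acceptability, together with concerns specific to this population; it does not name accuracy. The paired values will exist and can be compared at any time, so the information is not lost. The proposed estimates would carry no significance claim, so fixing them in advance protects little. They would also come from in-person sessions, with the week 0 pairs already filtered by the screen-failure rule, so they would not directly validate unsupervised or coached readings at home.

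**Conclusion.** No change to the plan is needed. The observation is accurate in a limited form: the spirometry values have no named analysis, while the completion of spirometry does. Device agreement and lung function are not stated objectives, and every stated aim can be answered by following the plan as written.

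What is missing is an optional descriptive analysis. With 15 participants it would fix the mean device difference to within ±0.55 SD and each limit of agreement to within ±0.97 SD, widening to ±0.72 and ±1.27 SD at 10 pairs. The documents give neither the SD nor the expected retention, so the figures are in SD units and the dropout cases are assumptions. The conclusion also rests on reading asthma control in Aim 3 as the Asthma Control Test. Analysts who wish to can tabulate the paired readings with the number of pairs and confidence intervals, labelled exploratory, or say in the report that the readings were not analysed.

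### An open-ended screen-failure ground, applied after consent, can remove likely non-completers before the pilot observes its participation outcomes

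*Combined protocol and SAP*

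**What the plan says.** Under Recruitment and Enrollment, the protocol lists entry and exclusion criteria. They include being able to follow directions for the study measures and having a mobile device with internet access. The target is 15 participants, and it is not stated whether that is counted before or after screening.

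Study Procedures places the baseline tests after consent: "After completing consent/assent procedures during study visit 1, baseline study procedures including standard spirometry using clinic-based pulmonary function equipment". It then sets the screen-failure grounds. The first is spirometry: "If participants are unable to complete reliable spirometry (either standard or mobile after 8 attempts and meet standard ATS criteria for acceptable technique". The others apply if participants "are unable to understand study measures, or if there are any other concerns about participation, the participant will be considered a screen failure". The sentence ends by requiring that reasons be kept: "the participant will be considered a screen failure and the reasons for screen failure recorded".

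The five remote visits use the mobile device: "Interval monthly visits at weeks 4, 8, 12, 16, and 20 will be completed using remote study procedures with completion of mobile spirometry". Table 1 schedules in-office spirometry at weeks 0 and 24.

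Statistical Considerations defines recruitment as consents among those approached, and retention as the "percent of enrolled participants who complete each study visit". It also plans the share needing extra training, the frequency of technical or connectivity problems, and an analysis of factors associated with finishing at least 80% of the measures. It does not define *enrolled*, and it plans no screen-failure rate.

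**The concern.** A discretionary screen-failure clause is unremarkable in a trial whose endpoint is something other than taking part. Here, taking part is the endpoint. A concern about participation raised at visit 1 is in effect a forecast of missed visits, technical trouble or heavy need for help, which are the events the study exists to count. Removing a child on that forecast selects on the outcome.

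Two things are at stake. One is the accounting: under one reading of *enrolled*, the removed child adds to recruitment and disappears from retention. The other is the information itself. Retraining need, connectivity problems and the factors linked to completion would be estimated from weeks 4 to 24 only in children whom staff chose to keep. The protocol presents this pilot as the step before large-scale studies in families with poor access to care, so flattering figures would carry forward.

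**Working it through.** The documents give no expected screen-failure rate, dropout rate or retention threshold, so there is no planned figure to reproduce. The check first traces a removed child through the outcomes, then compares denominators.

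**Step 1. Where a removed child appears**

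| Outcome | If *enrolled* means left after screening | If *enrolled* means consented |
|---|---|---|
| Recruitment | counted as a success | counted as a success |
| Retention | not in the denominator | in the denominator, as not retained |
| Retraining and connectivity, weeks 4 to 24 | never observed | never observed |

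The first reading can flatter retention. The second does not, but it mixes staff decisions with family dropout. The last row is the same under both.

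**Step 2. Denominator effect with 15 consented**

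Inputs: 15 from Enrollment targets, taken here as the number consented; *s* screen failures and *d* = 2 later dropouts, both assumed.

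- Post-screen retention = (15 − s − d)/(15 − s)
- All-consented retention = (15 − s − d)/15

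| s | Post-screen | All consented | Gap (points) |
|---|---|---|---|
| 0 | 13/15 = 86.7% | 13/15 = 86.7% | 0 |
| 1 | 12/14 = 85.7% | 12/15 = 80.0% | 5.7 |
| 2 | 11/13 = 84.6% | 11/15 = 73.3% | 11.3 |
| 3 | 10/12 = 83.3% | 10/15 = 66.7% | 16.7 |

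**Step 3. The same with 15 taken as the number left after screening**

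Post-screen retention is (15 − 2)/15 = 86.7% throughout. All-consented retention is 13/(15 + s): 13/16 = 81.2%, 13/17 = 76.5% and 13/18 = 72.2% for s = 1, 2 and 3. The gaps are about 5, 10 and 14 points.

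**Step 4. What these gaps are**

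They show the effect of the choice of denominator. They do not estimate bias, because the all-consented figure counts every removed child as not retained. Had the removed children stayed in the 15-consented case, retention would lie between (15 − s − 2)/15, if none of them completed, and 13/15 = 86.7%, if all did. For s = 2 the range is 73.3% to 86.7%, against a reported 84.6%; if one of the two completed, it is 12/15 = 80.0%. The post-screen figure is too high only if removed children would have completed less often than those kept. Removal for doubts about participation makes that plausible, but the documents give no figure for it.

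**The case against.** The strongest reply has four parts.

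- **Reasons are recorded.** The number and type of removals can be recovered and retention recalculated. This stands for the count. It does not stand for the rest: a log of reasons cannot supply outcomes at weeks 4 to 24 that were never observed, and the analysis section does not commit to reporting the log.
- **The retention effect hangs on an undefined word.** If *enrolled* means consented, the inflation does not occur. This stands, and it is why the point says that the rule can flatter retention. A reader might infer that retention will be inflated; the text does not support that.
- **Misuse is conjecture.** The open ground might be meant for doubts about assent or for safety, and nothing says that staff will use it to drop families expected to miss visits. Some grounds also overlap listed criteria, such as following directions and internet access. This stands too. The defect is that the wording permits such removals, and legitimate uses can be listed.
- **The pilot is too small for gaps of this size to matter.** The exact 95% interval for 13/15 is 59.5% to 98.3%, and no threshold is stated that a shift could cross. This is fair on precision. A selection effect is a separate problem from sampling error, however, and the interval does not cover it.

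A reader might also infer that the rule wrongly excludes children who manage the mobile device but fail the in-office test, since the remote visits use only the mobile device. The documents do not support that as an error. The wording "If participants are unable to complete reliable spirometry (either standard or mobile after 8 attempts" can mean failing either test or failing both. The study is a hybrid one in which in-office spirometry is a scheduled measure at weeks 0 and 24. Requiring it at entry is a design choice open to the sponsor.

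**Conclusion.** The concern holds for the open-ended ground. As written, it lets staff remove a consented child for a reason that anticipates the outcomes being measured, and the analysis plan neither counts such removals nor keeps them in a denominator. The effect on reported retention depends on *enrolled* meaning those left after screening and on removed children being less likely to complete. Its size cannot be estimated from the documents. Under the assumed 2 dropouts, one or two screen failures separate the two denominators by about 6 and 11 points if 15 is the number consented, or about 5 and 10 points if 15 is the number left after screening. The loss of information on retraining and connectivity does not depend on how *enrolled* is defined.

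The pilot can run without the change, but its feasibility figures would be harder to trust. For the spirometry ground, only the ambiguity of the wording is established.

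**What to change.** 1. In Study Procedures, replace the open ground with a closed list: consent or assent withdrawn, a listed entry or exclusion criterion found not to be met, or a safety reason. State that expected poor attendance or need for coaching is not a ground, and that expected poor connectivity is not one where the listed device and internet criterion is met.
2. In Statistical Considerations, define *enrolled* and say whether the target of 15 is counted before or after screening.
3. Report the number of screen failures by reason, and give retention with all consented children as the denominator beside the post-screen figure.
4. Separately, state whether the spirometry ground means failing either test or both. Whether in-office failure alone should exclude a child is for the sponsor to decide.

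The cost is protocol wording and a few extra lines of reporting from reasons already being recorded. Reported retention may be slightly lower, and staff lose some discretion at visit 1.

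### Acceptability rests on a questionnaire given only at study visits, with no exit form and no rule for children who miss visits or leave, so it may be overstated if dissatisfied children leave

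*Combined protocol and SAP*

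**What the plan says.** The Overview of the Study makes acceptability one of the three things the pilot is meant to determine. Under Statistical Considerations, "the Satisfaction and Usability Survey will be reviewed at the item-level", and responses of agree or strongly agree "will be used as benchmarks of acceptability and feasibility of each item". Open-ended answers on the same form are examined for themes. No other source of acceptability data is named.

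On timing, Study Procedures states: "The study-specific Satisfaction and Usability Questionnaire will be completed at each visit". Table 1 marks the "Satisfaction and Usability Questionnaire" at weeks 4, 8, 12, 16, 20 and 24 and leaves week 0 blank, so text and table differ on baseline.

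Retention has an explicit denominator: it is the "percent of enrolled participants who complete each study visit". Acceptability has none.

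Reasons are captured in two places, both in Study Procedures. If a child cannot take part at baseline, "the participant will be considered a screen failure and the reasons for screen failure recorded". At visits, "Reasons for inability to complete the mobile spirometry (e.g. technical concerns, patient effort) will be recorded at each visit". Nothing is said about recording why a child withdraws or stops attending. The enrollment target is "15 participants".

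**The concern.** A family that finds remote monitoring burdensome or unhelpful may well stop attending. The plan collects the child's opinion only at visits, so that opinion can be lost just when it is most informative. The open-ended answers come from the same respondents and do not fill the gap.

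Two things are at stake. First, an item percentage based on whoever answered may look better than the view of all the children who were offered the program. Second, because the denominator, visit and handling of repeated forms are left open, several quite different figures could be reported from the same 15 children, and the choice could be made after the data are seen. The analysis text can be repaired late. A leaver's opinion and reason for leaving cannot readily be recovered once the pilot is over.

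**Working it through.** The plan states no acceptability figure, target or dropout rate, so there is nothing to reproduce. The check asks how far the reported figure could depend on what is left unspecified.

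**Inputs.** From the documents: N = 15 enrolled and six scheduled questionnaires per child (Table 1). Assumed: d, the number of leavers with no usable form, from 0 to 5; and a, the number agreeing with an item among the 15 − d who respond.

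**Three readings of the same data**
- Responders only: a/(15 − d)
- All enrolled, leavers counted as not agreeing: a/15
- All enrolled, leavers counted as agreeing: (a + d)/15

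The gap between the first two is a/(15 − d) − a/15 = a·d/[15(15 − d)]. It is largest when every responder agrees (a = 15 − d), where it equals d/15. That is 1/15 = 6.7 points per leaver, 3/15 = 20.0 points for three and 5/15 = 33.3 points for five.

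| d (assumed) | a of responders | Responders only | Leavers not agreeing | Leavers agreeing |
|---|---|---|---|---|
| 0 | 15 of 15 | 100% | 100% | 100% |
| 1 | 14 of 14 | 100% | 14/15 = 93.3% | 15/15 = 100% |
| 3 | 12 of 12 | 100% | 12/15 = 80.0% | 15/15 = 100% |
| 3 | 11 of 12 | 91.7% (61.5 to 99.8) | 11/15 = 73.3% (44.9 to 92.2) | 14/15 = 93.3% |
| 5 | 10 of 10 | 100% | 10/15 = 66.7% | 15/15 = 100% |
| 5 | 9 of 10 | 90.0% (55.5 to 99.7) | 9/15 = 60.0% (32.3 to 83.7) | 14/15 = 93.3% |

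Brackets are exact (Clopper-Pearson) 95% intervals. In the last column the responder-only figure is never too high. With three leavers who would have agreed, 91.7% is slightly below 93.3%.

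**Children who leave after answering.** These children do have data, so the result depends on how repeats are combined. Suppose 3 of 15 leave after one unfavourable week-4 form, and the other 12 complete all six forms and agree each time.
- Week 4 alone: 12/15 = 80%
- Week 24 alone: 12/12 = 100%
- All forms pooled: (12 × 6)/(12 × 6 + 3) = 72/75 = 96%
- Last form per child: 12/15 = 80%

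With 5 such leavers, pooling gives (10 × 6)/(10 × 6 + 5) = 60/65 = 92%, against 10/15 = 67% by child. Pooling keeps the leavers' answers but gives each stayer six times the weight of an early leaver.

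**Children lost before week 4.** By Table 1 they give no form at all. If the text of Study Procedures is followed instead and a form is completed at week 0, it would precede any home use of the device.

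**The case against.** The strongest reply is that the plan is silent rather than wrong. A reader might infer that it restricts acceptability to children still attending, and that the resulting percentage is therefore overstated. The documents do not support that. No denominator, pooling rule, target or headline percentage is stated for acceptability. Six questionnaires are scheduled, so a child who leaves after week 4 has already answered, and nothing discards those answers. The direction of bias is also not shown: no dropout rate or reason for leaving is given, and families may leave for unrelated reasons. All of this stands, and it limits the point to a gap that may cause bias.

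A second reply is that attrition will be visible anyway. Per-visit retention among enrolled children is reported, as are spirometry success, retraining and connectivity problems, and factors related to completing at least 80% of measures are examined. This is partly right. Those figures show how many leave and some of the difficulties met. They do not show what leavers thought of the program or why they left, and they do not alter the item percentages.

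A third reply is that counting every non-responder as not agreeing merges acceptability with retention and treats a missed visit as dissatisfaction. That is fair. The all-enrolled figure suits a lower bound, not the sole basis for a conclusion.

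**Conclusion.** The concern holds as a gap in data collection and specification. Questionnaires come only from visits; there is no exit form, no recorded withdrawal reason, and no denominator or rule for missing forms. Acceptability may be overstated if dissatisfied children leave.

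The 6.7 points per leaver (20 with three, 33 with five) is an upper limit. It assumes that every responder agrees, that each leaver gives no usable form, and that each would have disagreed. The effect is zero with no leavers, and there is no overstatement if the leavers would have agreed. The number of leavers is assumed throughout. Where leavers have answered at least once, the size depends on a combining rule that the plan does not give; in the assumed example with three leavers it is 96% against 80%.

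This does not invalidate the pilot. It is a cheap improvement, best made while children can still be asked.

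**What to change.** 1. Offer any child who withdraws the same 5-minute questionnaire and a question on the reason for leaving, and record both.
2. Summarise each item once per child, using the last available questionnaire and including the exit form. By-visit figures can be shown as well. A last form completed before a child decided to leave may be more favourable than the exit view, so this step works best together with the first.
3. For each item, report agreement among responders beside agreement among all enrolled with non-response counted as not agreeing. Label the second a conservative lower bound, and draw the acceptability conclusion from the range.

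The same edit should say who counts as enrolled (in particular, whether baseline screen failures do) and should reconcile the text of Study Procedures with Table 1 on whether the questionnaire is given at week 0.

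The cost is a few lines of analysis text and one short form at withdrawal. The reported acceptability may be less favourable.
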